3.3. DLT Definition

Severity of AEs will be graded according to CTCAE v 4.03. For the purpose of dose escalation, any of the following adverse events occurring during the DLT observation period (first 2 Cycles, ie, 6 weeks) that are attributable to one or both study drugs will be classified as DLTs:

- Hematologic:
 - Grade 4 neutropenia;
 - Febrile neutropenia, defined as absolute neutrophil count (ANC) $<1000/\text{mm}^3$ with a single temperature of >38.3 degrees C (101 degrees F) or a sustained temperature of ≥ 38 degrees C (100.4 degrees F) for more than one hour;
 - Grade ≥ 3 neutropenic infection;
 - Grade ≥ 3 thrombocytopenia with bleeding;
 - Grade 4 thrombocytopenia.
- Non-hematologic:
 - Grade ≥ 3 toxicities (non-laboratory);
 - Grade ≥ 3 nausea, vomiting or diarrhea despite maximal medical therapy;
 - Grade 4 aspartate aminotransferase (AST) and alanine aminotransferase (ALT).
- Other (non AST/ALT) non-hematologic Grade ≥ 3 laboratory value if:
 - Medical intervention is required to treat the patient, or
 - The abnormality leads to hospitalization.

- Inability to complete two infusions of MK-3475 and PF-05082566 during the DLT observation period.

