3.2. Criteria for Dose Escalation

No dose escalation of MK-3475 is foreseen for the estimation of the combination MTD. Dose escalation and de-escalation of PF-05082566 will follow the Time-to-Event Continual Reassessment Method (TITE-CRM) (Cheung and Chappell, 2000)³ up to 5.0 mg/kg. The first three patients (first cohort) will be treated at the starting dose. For each subsequent patient, the probability of DLT is estimated for each level based on all the collected data from all treated patients up to that time and the prior expectations of toxicity, and the patient is assigned to the currently estimated target level (with escalation restrictions as indicated

below), defined as the dose having an estimated probability of DLT closest to but not greater than the target rate (25%). The probabilities of toxicity are estimated based on a Bayesian statistical model to learn about the overall dose-toxicity relationship. Patients' DLT data will be reported to the study statistician who will update the dose-toxicity model before the next enrolled patient is treated.

The MTD is defined as the highest combination dose with a DLT rate <25% from the model estimate (explained in [Section 9.2](#)).

Dose escalation stops if:

- Maximum sample size (n=45, see [Section 9.3](#)) is reached; or
- 9 evaluable patients have been treated at the estimated MTD; or
- All doses appear to be overly toxic and the MTD cannot be determined in the current trial.

In the TITE-CRM paradigm, patients who have enrolled in the trial, but have not experienced DLT, will be included in the probability calculation with an initial weight equal to the proportion of the 6-week (2 cycles of PF-05082566 and MK-3475) DLT observation period that the patients have completed (however, the weight function may be modified if accumulating safety data in suggest a different pattern). Patients who experience DLT or complete the observation period without DLT will be assigned full weight (=1). Details on the TITE-CRM method are provided in [Section 9.2](#) and the Statistical Analysis Plan.

To avoid overly rapid escalation and to retain the efficiency of dose administration when enrollment is fast, the following restrictions and practical considerations will be followed.

- Dose skipping in escalation to untested doses is not allowed ($k \rightarrow k+1$). In particular, at least three patients should have been treated at dose level k before escalation to dose level $k+1$;

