- At least three patients should have been on treatment (for a minimum of 3 weeks or 1 cycle) and observed DLT rate <33% at dose level k before a patient is assigned to dose level $k+1$ (*Note that the waiting window depends on our knowledge in the time-to-event pattern of toxicity and accumulating safety data, and thereby the confidence in the associated weights. However, intentional delay in enrollment in the absence of DLT or serious AEs should be minimized and discouraged*);
- Dose escalation recommendation by the TITE-CRM algorithm may be overruled by the sponsor if the nature of the existing data causes safety concern.

Dose escalation and de-escalation will be carried out according to [Table 1](#). Intra-patient dose escalation will not be permitted.

Cumulative safety data will continue to be evaluated at the estimated MTD using the Bayesian statistical model. Should emerging data in the expansion cohort indicate the selected dose is more toxic than previously estimated (>25%), or in the case of an exposure plateau or biomarker saturation (eg, sCD137) the next lower dose or an intermediate dose level will be explored, and may be declared as the RP2D.

For the first cohort there will be a minimum 7-day window between the first dose of a patient and the first dose of the next patient. For the first 3 patients enrolled in additional dose escalation cohorts, a minimum 24-hour time window will apply between their first doses. There will be no required time window between first doses for patients enrolled in dose cohorts with at least 3 previously treated patients.

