indicate a possible immune-related ECI, then additional testing should be performed to rule out other etiologic causes. If no other cause is found, then it is assumed to be immune-related.

ECIs that occur to any patient from the date of first dose through 90 days following cessation of treatment, or the initiation of a new anticancer therapy, whichever is earlier, whether or not related to the Sponsor's product, must be reported within 24 hours to the Sponsor either by electronic media or paper. Sponsor Contact information can be found in the administrative binder.

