9.7. Data Safety Monitoring Committee

An external Data Safety Monitoring Committee will not be established for this study. For the purpose of this protocol, Pfizer procedures for periodic safety review will be applied by an internal safety review team consisting of physician, safety specialist, and statistician to review individual and summary data collected in the safety and clinical databases. Procedures include:

- Surveillance for SAEs according to regulatory guidelines;
- Discussions between the Investigators and the Sponsor of AEs, laboratory test abnormalities, vital signs, and ECG findings observed at each dose level in an ongoing manner at regular teleconferences and/or meetings to determine the safety

profile and make a benefit/risk assessment and decide if further enrollment is appropriate;

- Findings having immediate implication for the management of patients on study will be communicated to all Principal Investigators in the timeframe associated with unexpected and drug-related SAEs.

During the dose-escalation phase, a Dose-Escalation Steering Committee (DESC) will be established to perform periodic review of the accumulating safety data, specifically, the DLTs. The guidance for dosing and enrollment decisions is based on the Bayesian statistical model of TITE-CRM. Other considerations may include lower grade AEs, nature and timing of the AEs, existing PK/PD data that may cause safety concerns. Following each review, the DESC will inform the study team and participating investigators on dosing and enrollment decisions. A DESC Charter will be prepared and will be available before the first DESC meeting.

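### The DLT list has no criterion for attributable Grade 4 or fatal anemia or hemolysis, so such an event after the second infusion enters the dose model as a non-DLT

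*Protocol*

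**What the plan says.** Protocol 3.3 defines a DLT as any listed event in the first two cycles (six weeks) that is attributable to one or both drugs. SAP 3.1 repeats the list.

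- **Hematologic items (five):** "Grade 4 neutropenia", febrile neutropenia, Grade 3 or higher neutropenic infection, Grade 3 or higher thrombocytopenia with bleeding, and Grade 4 thrombocytopenia.
- **General clinical item:** Grade 3 or higher non-laboratory toxicity, placed under the non-hematologic heading.
- **General laboratory item:** it opens "Other (non AST/ALT) non-hematologic Grade", so hematology values are outside it.
- **Missed-dose item:** "Inability to complete two infusions of MK-3475 and PF-05082566 during the DLT observation period".

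Protocol 3.2 gives weight 1 to patients who have a DLT or "complete the observation period without DLT will be assigned full weight". Other patients count for the fraction of the six weeks completed. Escalation from level k needs at least three patients with three weeks on treatment and an observed DLT rate below 33% at k. The model assigns the dose whose estimate is closest to, but not above, 25%.

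**The concern.** The list is closed, and red-cell toxicity appears nowhere on it. A life-threatening fall in hemoglobin attributed to treatment is not a DLT in itself, although its neutrophil and platelet counterparts at Grade 4 are.

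DLT is the primary endpoint and the only toxicity the dose model sees. A patient who has such an event and completes six weeks counts at full weight as evidence that the dose is tolerable. If that patient is one of the first three at a level, the written rules can permit a step up that they would refuse had the event been scored.

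**Working it through.** **1. Which routes could still make the event a DLT?**

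- *Before infusion 2.* Mostly covered. For events of clinical interest, Protocol 7.1.2.1 says: "If no other cause is found, then it is assumed to be immune-related". Table 9 discontinues treatment for a Grade 4 immune-related event, so infusion 2 is missed, and that is a DLT. A death before infusion 2 is caught the same way. What remains is an event not handled as immune-related that recovers in time for infusion 2. The re-treatment thresholds in 5.3.6 name neutrophils and platelets but not hemoglobin.
- *After infusion 2 (about Days 22 to 42).* The missed-dose item can no longer apply. Only a separate qualifying non-hematologic event would count.
- *Elsewhere.* Footnote 10 of the Schedule of Activities calls for counts at least every other day after a Grade 4 hematologic event, to look for DLTs, but adds no criterion. Table 8's hematologic row is keyed to the 3.3 list and so inherits the omission.

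**2. Model and inputs (Protocol 9.2, SAP 5.1.2).**

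- F_i(β) = p_i^exp(β), with β ~ N(0, 1).
- Example prior p = (0.01, 0.04, 0.08, 0.16, 0.25, 0.35) for 0.20, 0.45, 0.9, 1.8, 3.6 and 5 mg/kg.
- Likelihood: each DLT contributes F; each non-DLT contributes 1 − wF.
- The posterior mean of β is put back into F.
- Check on the set-up: exp(±1.65) = 0.192 and 5.207, matching the plan's 90% interval of 0.19 to 5.21.

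**3. Scenario (assumed).** No DLT in three full-weight patients at each level from 0.45 mg/kg to just below k. One late red-cell event among the first three at k, and no other DLT.

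Worked case, k = 0.45 mg/kg:

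- Scored (1/3): mean β = −0.803, exp(β) = 0.448. F(0.45) = 0.04^0.448 = 0.236 and F(0.9) = 0.08^0.448 = 0.322. The model stays at 0.45.
- Not scored (0/3): mean β = 0.377, exp(β) = 1.458. F(0.9) = 0.08^1.458 = 0.025. Escalation to 0.9 is allowed.

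Estimate at the level above k, all patients at full weight (target 0.25):

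| k (mg/kg) | Not scored, 0/3 | Scored, 1/3 | 1/4 | 1/5 | 1/6 |
|---|---|---|---|---|---|
| 0.45 | 0.025 | 0.322 | 0.278 | 0.244 | 0.218 |
| 0.9 | 0.037 | 0.281 | 0.255 | 0.233 | 0.215 |
| 1.8 | 0.048 | 0.257 | 0.236 | 0.218 | 0.203 |
| 3.6 | 0.064 | 0.255 | 0.237 | 0.221 | 0.206 |

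With 1/3, F(k) is 0.236, 0.174, 0.166 and 0.165, so the model keeps level k each time. At 5 mg/kg, F(k) is 0.171 scored and 0.037 not scored, and both stay at 5 mg/kg.

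**4. The observed-rate gate.** 1/3 = 33.3% fails the below-33% rule and 0/3 passes. This needs no prior. 1/4 = 25% passes.

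**5. Partial follow-up.** If the other two patients are only at three weeks (weight 0.5), F at the next level for k = 0.45, 0.9, 1.8 and 3.6 is 0.406, 0.321, 0.286 and 0.280 scored. Not scored, with all three at 0.5, it is 0.044, 0.050, 0.063 and 0.080. The split is the same. In the scored run at 0.45 mg/kg, F(k) = 0.317, so the model would point down to 0.20 mg/kg until the other two complete follow-up.

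**6. Fatal event.** A patient who dies on Day 30 has weight 30/42 = 0.714, not 1. At k = 0.45 the not-scored F(k) is then 0.010 instead of 0.009.

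**The case against.** - *Severe cases may be caught anyway.* Life-threatening anemia will often bring a Grade 3 or higher clinical event, and hemolysis may bring a Grade 3 or higher bilirubin needing intervention. Either counts. The protocol does not define hematologic, so some readers might place clinical hemolysis under the non-laboratory item. This narrows the gap, but that item's heading points the other way, and the coding of the primary endpoint should not rest on a reading.
- *People would notice.* Life-threatening SAEs are reported immediately (8.14.1). Section 3.2 says "intentional delay in enrollment in the absence of DLT or serious AEs should be minimized and discouraged", so a serious AE is an accepted reason to wait. The model's recommendation "may be overruled by the sponsor if the nature of the existing data causes safety concern". Section 9.7 has the steering committee look beyond DLTs: "Other considerations may include lower grade AEs, nature and timing of the AEs". This stands as a real safeguard for patients. It is discretionary, and it leaves the event coded as a non-DLT.
- *Timing.* The scenario needs the event before the next patient goes above k. With starts 24 hours apart, the third patient reaches three weeks when the first is at Day 24, two days after infusion 2. With fast accrual many late events would therefore come after escalation was already permitted. This stands. In the first cohort, with 7-day spacing, the first patient is at Day 36 when the gate can open, so two weeks of exposure after infusion 2 fall before it.
- *No signal.* The mouse surrogate study (1.2.7) reports white-cell and platelet effects, and the clinical background (1.2.8, 1.2.9.1) reports no red-cell signal. That bears on likelihood, not on how an event would be scored.

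**Conclusion.** The concern holds as a modest design point worth considering. Both documents leave attributable Grade 4 or fatal anemia or hemolysis off a closed DLT list. After infusion 2, nothing in the rules scores it unless a separate qualifying event occurs.

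The consequence is local. For one such event among the first three patients at 0.45, 0.9, 1.8 or 3.6 mg/kg, scoring holds the dose and not scoring allows escalation. At full weight the hold would lift after two further DLT-free patients at 0.45 or 0.9 mg/kg and after one at 1.8 or 3.6 mg/kg. With six patients and no other DLT the decision is the same either way.

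The model figures assume the example prior, clean lower levels and linear weights. The split at the observed-rate gate does not depend on the prior. No event rate and no change in the final MTD are claimed.

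**What to change.** Add one hematologic bullet to Protocol 3.3 and SAP 3.1: Grade 4 or higher anemia or hemolysis, subject to the existing attribution requirement. Table 8's hematologic row then applies without further editing.

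No new data are needed, because hematology is already weekly in the DLT window. The price is an occasional hold of one or two patients. If the event comes at 0.45 mg/kg while the other two patients are still in follow-up, there may be a temporary step down to 0.20 mg/kg.

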3.5. Dose Expansion Test Dose

The Expansion Test Dose will be either the estimated MTD or a lower dose if emerging data suggest the estimated MTD is more toxic than originally believed.

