3.7. Recommended Phase 2 Dose

The RP2D is the dose of PF-05082566 and MK-3475 in combination chosen for further study based on Phase 1 results. If the MTD proves to be clinically feasible for long term administration in a reasonable number of patients, such dose usually becomes the RP2D. Once the MTD is estimated, additional patients may be enrolled at this dosing level. In the expansion cohort, patients' DLT data will be entered into the Bayesian statistical model of the TITE-CRM procedure. If the posterior distribution of the model incorporating the additional data from the expansion cohort suggests the estimated MTD is associated with a higher than expected DLT rate the next lower dose or an intermediate dose level will be expanded, and may be declared as the RP2D.

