5.3.6. Dose Delays

Re-treatment following treatment interruption for treatment related toxicity or at the start of any new cycle may not occur until all of the following parameters have been met:

- ANC $\geq 1,000/\mu\text{L}$;
- Platelet count $\geq 75,000/\mu\text{L}$;

- Non-hematologic toxicities have returned to baseline or Grade ≤ 1 severity (or, at the investigator discretion, Grade ≤ 2 if not considered a safety risk for the patient).

If a treatment delay results from worsening of hematologic or biochemical parameters, the frequency of relevant blood tests should be increased as clinically indicated.

Withhold scheduled dose for liver function test (LFT) related AEs (including asymptomatic) Grade ≥ 3 until return to baseline or Grade ≤ 1 severity. In cases of potential liver injury, see [Section 8.6.2](#). In such cases, consultation with a hepatologist should be considered in the decision to initiate treatment with anti-inflammatory medications.

After all toxicities have recovered within the limits described above, treatment with PF-05082566 and MK-3475 can be resumed. Both study drugs should be delayed simultaneously. If non-hematologic toxicity does not resolve to Grade 1 (or Grade ≤ 2 if not considered a safety risk for the patient) within 9 weeks of last infusion, consider permanent discontinuation after consultation with the Sponsor. With investigator and Sponsor agreement, patients with a laboratory adverse event still at Grade 2 after 9 weeks may continue treatment in the trial only if asymptomatic and controlled. In addition, consider discontinuation for any severe or life-threatening event.

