8.6.2. Potential Cases of Drug-Induced Liver Injury

Abnormal values in aspartate transaminase (AST) and/or alanine transaminase (ALT) levels concurrent with abnormal elevations in total bilirubin level that meet the criteria outlined below in the absence of other causes of liver injury are considered potential cases of drug-induced liver injury (potential Hy's Law cases) and should always be considered important medical events.

The threshold of laboratory abnormalities for a potential case of drug-induced liver injury depends on the patient's individual baseline values and underlying conditions. Patients who present with the following laboratory abnormalities should be evaluated further to definitively determine the etiology of the abnormal laboratory values:

- Patients with AST or ALT and total bilirubin baseline values within the normal range who subsequently present with AST or ALT values ≥ 3 times the upper limit of normal (X ULN) concurrent with a total bilirubin value ≥ 2 X ULN with no evidence of hemolysis and an alkaline phosphatase value ≤ 2 X ULN or not available.
- For patients with preexisting ALT **OR**, AST **OR** total bilirubin values above the upper limit of normal, the following threshold values should be used in the definition mentioned above:
 - For patients with pre-existing AST or ALT baseline values above the normal range: AST or ALT values ≥ 2 times the baseline values and ≥ 3 X ULN, or ≥ 8 X ULN (whichever is smaller).
- **Concurrent with:**
 - For patients with pre-existing values of total bilirubin above the normal range: Total bilirubin level increased from baseline by an amount of at least 1 X ULN **or** if the value reaches ≥ 3 X ULN (whichever is smaller).

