The patient should return to the investigational site and be evaluated as soon as possible, preferably within 48 hours from awareness of the abnormal results. This evaluation should include laboratory tests, detailed history, and physical assessment. The possibility of hepatic neoplasia (primary or secondary) should be considered. In addition to repeating measurements of AST and ALT, laboratory tests should include albumin, creatine kinase, total bilirubin, direct and indirect bilirubin, gamma-glutamyl transferase, prothrombin time (PT)/international normalized ratio (INR), and alkaline phosphatase. A detailed history, including relevant information, such as review of ethanol, acetaminophen, recreational drug and supplement consumption, family history, occupational exposure, sexual history, travel history, history of contact with a jaundiced person, surgery, blood transfusion, history of liver or allergic disease, and work exposure, should be collected. Further testing for acute hepatitis A, B, or C infection and liver imaging (eg biliary tract) may be warranted. All cases confirmed on repeat testing as meeting the laboratory criteria defined above, with no other cause for liver function test (LFT) abnormalities identified at the time, should be considered potential Hy's Law cases irrespective of availability of all the results of the investigations performed to determine etiology of the abnormal LFTs. Such potential Hy's law cases should be reported as SAEs.

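### A drug-attributable, laboratory-only potential Hy's Law case can enter the TITE-CRM as a full-weight non-DLT; a combined liver criterion would be a cheap improvement

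*Protocol*

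**What the plan says.** Protocol 3.3 and SAP 3.1 carry the same DLT list. The only transaminase item is "Grade 4 aspartate aminotransferase (AST) and alanine aminotransferase (ALT". The rule for other Grade 3 or higher laboratory values leaves AST and ALT out and also requires intervention or hospitalization. The general Grade 3 item covers non-laboratory toxicity only. Failing to receive two infusions of both drugs within the six-week window is a separate DLT.

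Protocol 8.6.2 defines a potential Hy's Law case. With normal baseline values it is AST or ALT at least 3x ULN, bilirubin at least 2x ULN, no hemolysis, and alkaline phosphatase at most 2x ULN or unavailable. Such cases, absent another cause, "should always be considered important medical events". For those confirmed on repeat testing: "Such potential Hy's law cases should be reported as SAEs".

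Under Protocol 3.2, patients who experience a DLT or "complete the observation period without DLT will be assigned full weight (=1". Escalation also needs at least three patients on treatment at the current level "for a minimum of 3 weeks or 1 cycle) and observed DLT rate <33" percent. Protocol 3.5 allows the expansion dose to be "a lower dose if emerging data suggest the estimated MTD is more toxic than originally believed". In the expansion cohort, Protocol 3.7 says the patients' "DLT data will be entered into the Bayesian statistical model of the TITE-CRM procedure".

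**The concern.** Protocol 3.4 makes the MTD a model estimate, and the model sees only DLT or no DLT. A drug-attributed potential liver injury that matches no DLT item is not merely missing from that estimate. It counts as one more patient who tolerated the dose, and it pulls the estimated toxicity of every level down.

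The protocol watches the liver in other ways: eligibility limits, a dose hold for liver tests, a hepatic event of clinical interest and, in SAP 6.6.5.1, a tabulation of the combined criterion. Only the dose-finding endpoint lacks it. The prior signal is modest. Protocol 1.2.7 reports mild hepatic changes in mice given a surrogate antibody, and Protocol 1.2.8 reports only Grade 1 related events with the single agent at the data cut.

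**Working it through.** **1. Which cases slip through.** Four DLT routes already catch some potential Hy's Law cases:
- AST/ALT at Grade 4;
- bilirubin at Grade 3 or higher with intervention or hospitalization;
- a Grade 3 or higher clinical (non-laboratory) liver event;
- a missed second infusion. Protocol 5.3.6 makes this likely for a persisting Cycle 1 event: "Withhold scheduled dose for liver function test (LFT) related AEs (including asymptomatic", at Grade 3 or above.

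What remains is an attributable, laboratory-only case with AST/ALT below Grade 4, bilirubin below Grade 3 (or higher but neither treated nor hospitalized), and both infusions given. The plainest instance has onset after the second infusion, about Days 22-42. The dose hold then acts on Cycle 3, outside the window. The documents do not print the CTCAE cut-offs. With normal baseline values, the gap exists for any Grade 4 AST/ALT cut-off above 3x ULN and any Grade 3 bilirubin cut-off above 2x ULN.

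**2. Model, and the plan's own figure.** Protocol 9.2 gives F_i(β) = p_i^exp(β), with β ~ N(0, σ0²), σ0 = 1, and example priors 0.01, 0.04, 0.08, 0.16, 0.25, 0.35 for 0.20, 0.45, 0.9, 1.8, 3.6 and 5 mg/kg. Its 90% interval for exp(β), 0.19 to 5.21, reproduces: exp(±1.65) = 0.192 and 5.207 (exp(±1.645) gives 0.193 and 5.18). The likelihood is F for a DLT and 1 − wF for a non-DLT. The posterior mean of β is put into F, and a level is assignable if its estimate is not above 25%.

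**3. One case among three patients.** Assume full weights, three DLT-free patients at each lower level from 0.45 mg/kg, and no other DLT.

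| Case at | Next level | β uncounted → counted | Next-level estimate |
|---|---|---|---|
| 0.9 | 1.8 | 0.590 → −0.367 | 3.7% → 28.1% |
| 1.8 | 3.6 | 0.782 → −0.020 | 4.8% → 25.7% |
| 3.6 | 5 | 0.965 → 0.263 | 6.4% → 25.5% |

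First row: exp(−0.367) = 0.693 and 0.16^0.693 = 0.281. One in three is also 33.3%, which fails the 33% restriction if the case is known in time. A case on Days 22-42 may come after that check has been passed.

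At an interim look with partial weights (case on Day 30 at 0.9 mg/kg, two others there at 30/42, three full-weight at 0.45, one at 1.8 with 8/42), 1.8 mg/kg is at 29.9% counted and 4.2% uncounted. With σ0 = 0.5 the counted figure is 23.6%, so the hold is not universal.

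**4. How long the hold lasts.** As DLT-free patients are added at the level of the case, the next level falls: 28.1%, 25.5%, 23.3% (case at 0.9); 25.7%, 23.6% (1.8); 25.5%, 23.7% (3.6). One or two more patients release it. Over the whole path with a case at 0.9 and no other DLT, 3 + 5 + 4 + 6 = 18 patients are needed before 5 mg/kg opens, against 4 × 3 = 12 if it is not counted. Nine DLT-free patients at 5 mg/kg then give 15.1% there, so 5 mg/kg is still the MTD.

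**5. Final MTD.** Take nine patients at 0.9, 1.8 or 3.6 and three DLT-free at each lower level from 0.45. Use three skeletons (the example; 0.05, 0.10, 0.15, 0.25, 0.35, 0.45; and 0.01, 0.02, 0.05, 0.10, 0.18, 0.25) with σ0 = 0.5, 1 and 2: 3 × 3 × 3 = 27 combinations.
- Case as the only DLT: next level 13.6-24.6%, above 25% in 0 of 27.
- Case plus one other DLT: next level 20.7-30.7%, above 25% in 21 of 27, of which 10 are at or below about 26.2%. With the example skeleton and σ0 = 1, going from one to two DLTs moves the next level from 17.5% to 27.9% (nine at 0.9), 16.8% to 26.0% (nine at 1.8) and 17.3% to 26.0% (nine at 3.6).
- Nine at 5 mg/kg (example skeleton, σ0 = 1): the result changes only from three to four DLTs (23.3% to 28.9%).

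**The case against.** **Seriousness is not dose-limiting severity.** Protocol 8.8 separates severity from seriousness, and no document says every SAE must be a DLT. A reader might infer that the protocol contradicts itself, or that Hy's Law cases in general escape the DLT definition. Neither follows: the SAE rule and the DLT list serve different purposes, and four DLT routes catch part of these cases. This objection stands, and it limits the point to a design choice about a narrow group.

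**The plan can respond in other ways.** The waiting-window note in Protocol 3.2 discourages enrolment delay only when there is no DLT or serious AE, so it leaves room to pause for exactly this event. The sponsor may overrule an escalation. Under Protocol 9.7 the dose-escalation committee may weigh lower-grade events. A lower expansion dose or RP2D is possible. These are real safeguards, and a pause is all that counting a lone case would achieve in the settings checked. But they are discretionary, and nothing in the supplied text recodes the patient in the model. The committee charter and the guidance on events of clinical interest were not available, so that statement covers only the protocol and SAP.

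**The 21 of 27 is a static picture.** It holds nine patients at one level with nobody above. With one DLT among four at 3.6 mg/kg, 5 mg/kg is already at 23.7%, so later patients would normally move up and supply data there. It also needs a second DLT at the same level, and many crossings are slight. This stands.

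**The laboratory criteria are a screen.** Protocol 8.6.2 uses baseline-relative thresholds, and Protocol 4.1 exempts documented Gilbert syndrome from the bilirubin limit. Importing the screen unguarded could turn a modest bilirubin fluctuation into a DLT. This also stands, and the fix is worded to meet it.

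**Conclusion.** The gap is real and narrow, and worth closing because closing it is cheap. An attributable, laboratory-only potential Hy's Law case, below the DLT grades and with both infusions given, is an SAE under Protocol 8.6.2 and a full-weight non-DLT in the model.

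The effect is limited. A lone counted case slows escalation: one or two extra patients at that level, or six over the whole path for a case at 0.9 mg/kg with σ0 = 1. A reader might infer that leaving out a single case inflates the final MTD. The calculations do not support that (0 of 27). The final MTD can change when another DLT is present at the same level, under the static assumptions above.

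The figures rest on the protocol's example prior or the stated variants, assumed cohort data and, except at the interim look, full follow-up. The documents give no incidence, so the chance of any effect is unknown.

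**What to change.** In Protocol 3.3 and SAP 3.1, add as a DLT: *an event with onset in the DLT window that meets the Section 8.6.2 potential Hy's Law laboratory criteria, is confirmed on repeat testing, has no other cause identified (for example Gilbert syndrome, biliary obstruction, hepatic progression or viral hepatitis), and is attributable to one or both study drugs*. In the existing item, change *AST and ALT* to *AST or ALT*; this is a minor clarification.

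No new scheduled sampling is needed. AST, ALT, total bilirubin and alkaline phosphatase are in the chemistry panel (Protocol Table 4) and are drawn weekly in Cycles 1-2. Protocol 8.6.2 already requires repeat testing, and SAP 6.6.5.1 already derives the combination. The cost is a protocol amendment, because the primary endpoint definition changes (Protocol 9), plus an occasional extra DLT, some delay in escalation and possibly a lower MTD.
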